We expect that participants receiving NCT will exhibit improved core ADHD symptomatology and secondary and exploratory outcomes compared with waiting list controls. Moreover, we hypothesize differing effects of Cognitive training in ADHD type of NCT (SCP, Lzs, WMt) based on the participant characteristics (e.g. genetic predisposition, age, IQ, gender, verbal skills, and comorbidity) will predict patterns of treatment effects on the various outcomes. The sample size calculation refers to the three primary outcome endpoints: change in Conners 3 total scores and subscales for parent, self-report, and blind teacher ratings between baseline and follow-up assessment, in the Intention to Treat (ITT) sample. MANOVA for repeated measures (three measurement points, withinbetween subjects' interactions, posthoc tests) will be used for the statistical analysis for the RCT study. Based on available evidence about NCT efficacy medium effects for the primary outcomes are expected. With N=200 (n=50 SCP vs. n=50 Lzs vs. n=50 WMtr vs. n=50 TAU only controls) and alpha=5%, the power (1-beta) is >99% for medium effects (G Power 3.1.7). All data provided for the participants will be included in the analyses. Data will be tested for normality and homogeneity of variance. To verify that the treatment group and control groups are comparable for continuous and categorical demographic variables at pretreatment, a series of independent-samples t-tests and chi-square tests will be conducted. As for primary outcomes, analyses for secondary outcomes will be conducted according to ITT principles. To analyse for the significance of potential factors predicting outcomes (age, IQ, language abilities, gender, comorbidity, genetic variants) in the active NCTs training groups, these are analysed using a logistic regression to explain dichotomized (by median-split) Conners 3 outcomes as the dependent variable.

Adverse events

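### The between-arm analysis uses baseline Conners 3 only as a time point and adjusts for no covariate, so the pairwise comparisons are less precise than the collected data allow

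*Combined protocol and SAP*

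**What the plan says.** All of the relevant text is in the Statistical analysis section of the combined protocol and SAP.

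- **Primary analysis:** "MANOVA for repeated measures (three measurement points, withinbetween subjects' interactions, posthoc tests) will be used for the statistical analysis for the RCT study". No covariate is named.
- **Endpoint:** "change in Conners 3 total scores and subscales for parent, self-report, and blind teacher ratings between baseline and follow-up assessment", in the intention-to-treat sample.
- **Baseline comparability:** "a series of independent-samples t-tests and chi-square tests will be conducted". The purpose given for these tests is "To verify that the treatment group and control groups are comparable for continuous and categorical demographic variables at pretreatment". The variables, the number of tests and the significance level are not listed. No action follows a significant result.
- **Power:** "medium effects for the primary outcomes are expected", and with four arms of 50 and a 5% alpha "the power (1-beta) is >99% for medium effects (G Power 3.1.7"). No numerical effect size or correlation is given.

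Age, IQ, language abilities, gender, comorbidity and genetic variants appear as possible predictors, but only in a logistic regression within the active arms. The Randomization section mentions a random list and no stratification.

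**The concern.** Baseline Conners 3 enters the primary model as the first of three outcome measurements. For the contrast that the endpoint names, this gives the difference between arms in mean change. A change score gives the baseline value a fixed weight of one. Adjustment uses the regression weight, which is never less precise in large samples and is more precise whenever rho is below 1.

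The loss falls on the questions the trial most wants answered. The main hypothesis is training against waiting-list control, and the first key objective under Aims and objectives is whether the methods differ from each other. Both come down to comparisons of 50 v 50.

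The baseline tests do not fill this gap. With sound randomisation any difference they flag is chance. Their p-values do not show whether an imbalance matters for the outcome, and baseline Conners 3 is not named among the variables tested.

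**Working it through.** **Inputs.** From the Statistical analysis section: four arms of 50, three time points, alpha 5%. Assumed, because the documents do not give them: medium effect taken as f = 0.25 (omnibus) or d = 0.5 raw-score SD (pairwise); two-sided tests without multiplicity correction; equal variance at baseline and follow-up; no missing data; rho varied from 0.3 to 0.9; 3 to 10 baseline variables tested.

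**1. The plan's own power figure.** For the group-by-time interaction, the noncentrality is f² × N × m/(1−rho). At rho = 0 this is 0.0625 × 200 × 3 = 37.5, with (4−1)(3−1) = 6 and (200−4)(3−1) = 392 degrees of freedom. Power is 99.9%, and higher for any positive rho. If 0.25 is instead read on the MANOVA effect scale, the noncentrality is 200 × 2 × 0.0625 = 25 and power is 97.8%. The stated >99% reproduces on the first convention and is close on the second. It is the power of an omnibus test, not of a 50 v 50 comparison.

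**2. Variance with and without adjustment.** In units of the raw-score variance, the change score has variance 2(1−rho). The baseline-adjusted score has 1−rho² = (1−rho)(1+rho). The ratio is (1+rho)/2, whatever the effect size or its units.

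**3. Pairwise power.** Two-sample t, 50 v 50. The standardised effect is 0.5/√(2(1−rho)) for change and 0.5/√(1−rho²) after adjustment. The last column is 50 divided by the ratio: the arm size at which a change-score analysis would match the adjusted one.

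| rho | Variance ratio | Change-score power | Adjusted power | Equivalent n per arm |
|---|---|---|---|---|
| 0.3 | 0.65 | 55% | 74% | 77 |
| 0.5 | 0.75 | 70% | 82% | 67 |
| 0.7 | 0.85 | 89% | 93% | 59 |
| 0.8 | 0.90 | 97% | 98% | 56 |
| 0.9 | 0.95 | >99.9% | >99.9% | 53 |

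**4. Chance imbalance in the score itself.** If two arms differ by D at baseline by chance, the change-score contrast is shifted by (1−rho)D through regression to the mean. With D = 0.3 SD and rho = 0.5 the shift is 0.15 SD, or 0.15/0.5 = 30% of the assumed effect. By simulation, at least one of the three training-versus-control pairs differs by more than 0.3 SD in about 31% of sound randomisations. Averaged over randomisations the shift is zero, so it appears as lost precision and not as bias.

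**5. The baseline tests.** With three comparisons against one shared control arm, simulation gives about a 12.5% chance per variable of at least one p<0.05. For k independent variables the chance is 1−(1−0.125)^k: 33% for 3, 55% for 6 and 74% for 10. In the other direction, a true 0.3 SD difference between two arms of 50 reaches p<0.05 only 32% of the time.

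**The case against.** The strongest defence is that nothing here is invalid. Baseline Conners 3 is in the primary model, a change-score contrast is unbiased under randomisation, and the stated omnibus power is already near its ceiling. All of this stands. It limits the point to precision in the pairwise comparisons and does not remove it there. The size of the gain also depends on a correlation that the documents do not give, and at rho of 0.8 or more there is little to win.

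Three stronger readings are tempting, and the documents support none of them.

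- A reader might infer that significance tests have replaced the use of baseline data. They have not: the tests concern demographic variables and sit beside a model that contains the baseline score.
- A reader might infer that chance alarms would distort the result. The plan attaches no covariate selection, exclusion or change of model to them, so no planned estimate or p-value would change.
- A reader might take 10 variables × 3 comparisons as 30 independent tests and arrive at 1−0.95^30 = 79%. The plan lists no variables, and comparisons that share a control arm are not independent, so a range is all that can be given.

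One could also keep the tests as a check on allocation, since the Randomization section is so brief. That is not the purpose the plan states, and the 32% detection rate shows how weak such a check would be.

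**Conclusion.** The point holds as one of efficiency. The planned between-arm analysis is unbiased under randomisation but leaves its contrasts with more variance than necessary: adjusted variance would be 65% to 95% of the change-score variance for rho from 0.3 to 0.9. In pairwise power that is worth about 18 percentage points at rho 0.3, 12 at 0.5, 4 at 0.7, 1 at 0.8 and nothing at 0.9. These figures rest on d = 0.5 in raw SD units, complete data and two-sided 5% tests. The equivalence to a change score is exact for the baseline-to-follow-up contrast, which is the endpoint the plan names. The calculation covers adjustment for the baseline score only; no gain has been established for any other covariate. The baseline tests are uninformative for their stated purpose, but this is secondary because nothing depends on them.

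**What to change.** Before outcome data are examined, prespecify a primary model for each informant's Conners 3 score that adjusts for the same informant's baseline score. Baseline can be a covariate, or it can be constrained equal across arms in a repeated-measures mixed model. State the training-versus-control and method-versus-method contrasts to be taken from it. Name any further covariates, such as age, in advance and choose them from variables already collected. Replace the t-tests and chi-square tests with a descriptive baseline table by arm that includes Conners 3.

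No new data, visits or participants are needed. The cost is a few degrees of freedom, negligible against about 196 for error (200−4), and a documented, dated change to the primary analysis. It is more than a wording change, because the Trial status section reports that enrolment began in August 2013.

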**A Comparative Randomized Controlled Pragmatic Trial of
Neurofeedback and Working Memory Training for Children with
Attention-Deficit/Hyperactivity Disorder: Protocol**

Abstract

Today, the treatment for children and adolescents with Attention Deficit/Hyperactivity Disorder (ADHD) is predominantly pharmacological. However, not all individuals respond to medication or experience side effects. In addition, the compliance and treatment fidelity to medication is sometimes limited, why effective non-pharmacological treatment options are desirable. Neurocognitive training (NCT) methods such neurofeedback (NF) and working memory (WMt) have shown efficacy to treat the primary symptoms of ADHD in non-blinded trials. Still, larger, comparative and blinded pragmatic randomized trials are needed to ensure their efficacy and effectiveness, and to identify an optimal training rationale. Furthermore, little is known about predictors of treatment response to NCTs, such as genetic variants. In this article we present the protocol of a randomized controlled pragmatic trial. Three NCT methods, namely two NF variants, Slow Cortical Potential training (SCP), and Live Z-Score training (LZS), as well as Working Memory Training (WMt) are evaluated against each other and a waiting list control/treatment as usual only group. In a clinical outpatient setting, N = 200 children and adolescents with ADHD aged 9-17 years and common comorbidities are randomized to one of the treatment groups or the inactive control group (n=50/group). The treatment groups (SCP/LZS/WMt) receive a total of 25 highly frequent training sessions (5/week for 5 weeks). A comprehensive assessment comprising ADHD core symptoms, psychopathology, neuropsychology, neurophysiology, quality of life and health related measures are collected pre and post treatment as well as at a 6-month follow-up. Primary outcomes are blinded teacher and unblinded parent ratings as well as self-ratings on the Conners 3 for ADHD. We expect that participants receiving NCT will exhibit improved core ADHD symptomatology compared to waiting list controls. Moreover, we hypothesize that type of NCT (SCP, LZS, WMt) and participant characteristics, such as genetic predisposition, age, IQ, gender, verbal skills, and comorbidity predict patterns of treatment effects the various outcomes.

Key words: ADHD, ADD, comorbidity, attention, treatment, neurofeedback, working memory training, RCT, evidence-based, intervention

Study protocol

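### The predictor analysis uses only the active groups and states no factor-by-type term, so it cannot test whether participant characteristics modify treatment effects

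*Combined protocol and SAP*

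**What the plan says.** The Abstract states the hypothesis as "we hypothesize that type of NCT (SCP, LZS, WMt) and participant characteristics" predicting patterns of treatment effects. The Statistical analysis section repeats it in a garbled sentence: effects are to differ by training type "based on the participant characteristics (e.g. genetic predisposition, age, IQ, gender, verbal skills, and comorbidity"), and these "will predict patterns of treatment effects on the various outcomes". Under Aims and objectives, objective (ii) asks for predictors that tell learners from non-learners.

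The analysis of characteristics is one sentence at the end of the Statistical analysis section. It concerns "potential factors predicting outcomes (age, IQ, language abilities, gender, comorbidity, genetic variants") and reads: "in the active NCTs training groups, these are analysed using a logistic regression to explain dichotomized (by median-split) Conners 3 outcomes". The TAU arm is not in it, training type is not a listed regressor, and no product term is stated. The main analysis is a "MANOVA for repeated measures (three measurement points") with within-between interactions, that is, time by group. It names no characteristic. No other section gives a moderator or subgroup analysis.

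The Control section says that the control group is measured at the same time points as the active groups.

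**The concern.** A treatment effect in this trial is a contrast between arms: training versus TAU, or one training type versus another. A characteristic predicts a treatment effect when that contrast changes with the characteristic. The planned regression contains no such contrast. It relates characteristics to outcome among children who were all trained.

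Two questions are therefore left open. For effects against TAU, the missing arm is decisive. For differences between training types, TAU is not needed; what is missing is the factor-by-type term.

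At stake is how the result is reported. If a factor is associated with a better Conners 3 outcome among trained children, the hypothesis invites the report that it predicts the effect of training, although the same children might have improved without it.

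**Working it through.** **Inputs from the documents.** Four arms of 50 (150 active, 50 TAU); alpha 5%; three measurement points; six listed factors; power above 99% for medium effects.

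**Assumptions, not in the documents.** One factor at a time; baseline-adjusted score with normal errors and residual SD 1; slopes in SD of score per SD of factor; no dropout; two-sided tests; active arms pooled unless stated.

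**1. The plan's own figure.** For the time-by-group interaction, λ = f²·N·m/(1−ρ). With f = 0.25 taken for medium, N = 200, m = 3 and ρ = 0, λ = 0.0625 × 200 × 3 = 37.5. The degrees of freedom are 3 × 2 = 6 and 196 × 2 = 392. Power is 99.9%, and higher for ρ from 0.3 to 0.7, so the stated figure reproduces. (Other effect-size conventions for this test give roughly 75% to 98%.) It is power to compare groups over time and says nothing about characteristics.

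**2. What the planned model can see.** Let the factor's slope be β₁, β₂, β₃ in the three active arms and β₀ in TAU. Modification of the training-versus-TAU effect is mean(β₁, β₂, β₃) − β₀. The planned model never uses β₀, so it behaves identically whatever β₀ is. Simulated percentages of trials with a significant result (4,000 runs per row; the last row 2,000 runs):

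| Slopes, active arms / TAU | Planned model | Factor × (training vs TAU) |
|---|---|---|
| 0 / 0 | 5% | 5% |
| 0.3 / 0.3 (prognostic only) | 82% | 5% |
| 0.3 / 0 (true modifier) | 82% | 43% |
| 0 / −0.3 (modifier seen only against TAU) | 5% | 42% |

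A balanced binary factor worth 0.5 SD gives the same pattern: 71% against 5% when it acts in all arms, and 72% against 33% when it acts in trained children only.

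**3. Differences by training type.** The plan does not say whether the active groups are pooled or analysed separately. Take slopes of 0.3, 0 and −0.3 in the three types.
- Pooled: significant in 5% of trials. This is the worst case for pooling, because the slopes cancel.
- Separately by arm: 39%, 6% and 38%, with at least one arm significant in about 65%.
- Factor-by-type test (2 df): 74%.

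Separate tests do not rescue the by-type question. If the slope were 0.3 in all three types, each arm would be significant with probability about 0.39. The arms would then disagree with probability 1 − 0.39³ − 0.61³ = 1 − 0.059 − 0.227 = 0.71, with no true difference between types.

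**4. Power of the missing test, training versus TAU.** SE of the slope difference = √(1/150 + 1/50) = 0.163. For 80% power the difference must be (1.96 + 0.84) × 0.163 = 0.46 SD. For a balanced binary factor, divide by √(0.5 × 0.5) = 0.5, giving 0.91 SD. With 20% dropout (120 versus 40) these become 0.51 and 1.02 SD.

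**5. Number of tests.** Six factors with two interaction tests each make 12 per score. The chance of at least one false positive is 1 − 0.95¹² = 46% if the tests are independent, and at most 12 × 0.05 = 60%. Bonferroni over 12 would raise 0.46 SD to 0.61 SD.

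**The case against.** The strongest reply is that the hypothesis need not mean effect modification. The Abstract lists training type and characteristics side by side as predictors, with no explicit interaction. On that additive reading, the group comparison covers type and the regression covers characteristics. Other wording is about response: the Abstract notes that "little is known about predictors of treatment response to NCTs, such as genetic variants", and objective (ii) concerns learners. This stands as far as it goes: the regression fits objective (ii), and the hypothesis sentence is too garbled to settle the meaning. But patterns of treatment effects, and effects that differ by type according to characteristics, still point to effect modification. The plan should say which is meant.

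Second, the 82% is not an error rate. The model correctly detects a real association, and harm arises only if that is reported as effect modification. This also stands, and it is why part of the remedy is a reporting rule.

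Third, the plan is silent on interaction terms and does not exclude them. True, but silence leaves at least 12 tests per score to be chosen later.

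Fourth, interactions are underpowered here. They are. That argues for an exploratory label or for withdrawing the claim, since a better-powered model of another question does not answer this one.

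A reader might also infer that the median split wastes power. The documents do not give the score distribution, and the split can lose or gain depending on it, so no such claim is made.

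**Conclusion.** The point holds in a limited form. Read as effect modification, the hypothesis has no stated analysis: the active-group regression cannot separate prognostic from predictive factors, and no stated term tests whether a factor's effect differs by training type. The second conclusion holds whether the active groups are pooled or analysed separately.

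Two stronger readings are not supported. One is that the regression is purely prognostic. A factor found among trained children may be prognostic, predictive or both, and the design does not say which. The other is that the plan would almost always miss differences between types, as the 5% against 74% contrast might suggest. That contrast depends on pooling, which the plan does not state, and on slopes chosen to cancel.

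That the planned model cannot see the TAU slope follows from the design. The percentages rest on assumed slopes, normal errors, one factor and no dropout, and serve only as illustration. The plan should be changed here, but the primary comparison of arms is not affected.

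**What to change.** 1. Keep the active-group regression for objective (ii). State whether the arms are pooled, and report it as association among trained children that cannot separate prognostic from predictive factors.
2. For the treatment-effect hypothesis, add an exploratory model of the continuous Conners 3 follow-up score adjusted for baseline, in all four arms, with factor × (training versus TAU) and factor × training-type terms. The type terms can also be tested within the active arms. Name the rater and whether the total or a subscale is used.
3. Claim effect modification only from these interaction terms, with confidence intervals and the number of tests performed.

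No new outcome data are needed, because TAU is already measured at the same time points. The cost is a rewritten predictor paragraph and the likelihood that the hypothesis stays unresolved, given the detectable differences and test counts above.

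Minimum alternative: reword the hypothesis to match objective (ii) and state that effect modification is not tested. That costs a sentence or two and is proportionate if the sponsor does not want underpowered interaction tests.

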Guidelines recommend multimodal treatment combining psychosocial and educational interventions with medication. Compared with psychopharmacological treatment studies there are quite a limited number of studies on alternative treatments for children and adolescents with AD/HD²⁰. CLT's are non-invasive methods and above all NF has shown good preliminary evidence in several international studies in reducing the core symptoms of AD/HD in children, and has encouraging results in contrast to psychopharmacological treatment that the positive effect persists²¹. WMt has promising evidence of improving working memory capacity and that the good effects also can generalize into other functions but there are a clear shortage of studies comparing WMt with other active interventions and controls (Melby-Lervåg, 2012). If the results would be positive then CLT's could broaden the range of treatment for children and adolescents with AD/HD in Sweden. To date there are several different kinds of neurofeedback training options and two mainstream methods are Slow Cortical Potential training (SCPt) and frequency training (Ft) whereas the latter offers more commercially available options. For the clinical validity of this rather extensive training it is of major importance that potential improvements also last. There is a lack of follow-up studies concerning CLTs (Hodgson et al, 2012, Lofthouse et al, 2012, Melby-Lervåg et al, 2012) and the aim of this sub study is to measure long term outcome from CLT methods

Aims and objectives

Primary aim of the study is to evaluate if neurocognitive training improves core symptoms in AD/HD. Key objectives are (i) are there differences in outcome between the different neurocognitive methods, (ii) can we find predictors that differentiate learners from non-learners, (iii) are neurocognitive methods feasible in clinical settings. Additional important research questions are a) if possible improvements generalize to other settings like

school and home environment, b) does effects last six months after training, c) does the training affect the bioelectrical communication in the brain, d) are there more generalized beneficial outcomes as in perceived quality of life, stress in parents, sleep patterns.

Method/design

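### The median split of the Conners 3 outcome costs the predictor analysis power and ranks trained children only against each other, so it cannot show who improved

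*Combined protocol and SAP*

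**What the plan says.** The Aims and objectives section lists as key objective (ii): "can we find predictors that differentiate learners from non-learners". The Statistical analysis section gives a single analysis of predictors. Its population is "in the active NCTs training groups", its candidate predictors are "age, IQ, language abilities, gender, comorbidity, genetic variants", and its method is as follows: "these are analysed using a logistic regression to explain dichotomized (by median-split) Conners 3 outcomes as the dependent variable".

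The same section describes the primary endpoints on a continuous scale: "change in Conners 3 total scores and subscales for parent, self-report, and blind teacher ratings between baseline and follow-up assessment". Primary outcome measures likewise speaks of changes in core symptoms.

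The documents define neither learner nor responder, and they give no threshold for reliable or clinically important change on the Conners 3. The predictor sentence does not say which rater, scale or time point is split, and it does not repeat the word change.

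**The concern.** A cut at the sample median has two consequences.

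- **It throws away information.** Two children just either side of the median are treated as opposites, and two children far apart on the same side as identical. Real predictors become harder to detect.
- **It is relative to the sample.** About half the trained children are in the better half by construction, whether training helped nearly all of them or none. The cut has no link to an amount of change that means anything on the instrument.

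What is at stake is a named key objective. The plan could miss predictors that its own data would support, and any it does find could be reported as characteristics of children who learned, which the split does not establish.

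**Working it through.** **1. The plan's own power figure.** The plan states "alpha=5%, the power (1-beta) is >99% for medium effects (G Power 3.1.7". Medium is not given as a number, so f = 0.25 is assumed, with 4 groups, 3 time points and N = 200.

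- Repeated-measures group-by-time interaction: noncentrality = N × m × f² / (1 − ρ) = 200 × 3 × 0.0625 / (1 − ρ). At ρ = 0 this is 37.5, with df 6 and 392, and power is 99.9%. For ρ from 0.3 to 0.7 it is about 100%.
- Pillai MANOVA variant: noncentrality = N × s × f² = 200 × 2 × 0.0625 = 25, and power is 97.8%.

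The stated figure is therefore reproduced, but for the omnibus group comparison. No power is stated for the predictor analysis.

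**2. Number of children in the predictor analysis.** The plan has "With N=200 (n=50 SCP vs. n=50 Lzs vs. n=50 WMtr vs. n=50 TAU only controls". The controls are not in the predictor model, which leaves 3 × 50 = 150. This assumes that every trained child is analysed.

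**3. Information kept by the split.** The relative efficiency of a median split against a continuous analysis, for modest predictor effects, is 4 × f(median)² × variance, where f here is the outcome density. For a normal outcome this is 2/π = 0.637.

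- Information lost: 1 − 0.637 = 36%.
- Effective number: 150 × 0.637 = about 95 children.
- Number needed to match a continuous analysis of 150: 150 / 0.637 = about 236.

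The documents give no SD or distribution, so the result is shown for other shapes:

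| Outcome shape | Efficiency of split | Loss |
|---|---|---|
| Uniform | 0.333 | 67% |
| Normal | 0.637 | 36% |
| t, 10 df | 0.757 | 24% |
| Logistic | 0.822 | 18% |
| t, 5 df | 0.961 | 4% |
| Laplace | 2.0 | none |

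**4. Power for one continuous predictor.** The assumptions are n = 150, two-sided 5% (the plan does not state sidedness), a normal outcome and illustrative correlations r. For the continuous analysis, z = atanh(r) × √(150 − 3) = atanh(r) × 12.12. For the split, z is multiplied by √0.637 = 0.798. Power is about Φ(z − 1.96).

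| r | z, continuous | Power | z, split | Power |
|---|---|---|---|---|
| 0.20 | 2.46 | 69% | 1.96 | 50% |
| 0.25 | 3.10 | 87% | 2.47 | 70% |
| 0.30 | 3.75 | 96% | 2.99 | 85% |

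Simulations comparing a continuous analysis with logistic regression on the median split (2,000 or 3,000 trials per setting) agree to about one point: 70% against 50–51%, 87% against 70%, and 96% against 84–85%.

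For a binary predictor dividing the children 75/75, power falls from 45% to 31% at d = 0.3, from 69% to 49% at d = 0.4, and from 86% to 68% at d = 0.5.

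**5. What the label conveys.** If individual change is normal, the share of trained children who improve is Φ(mean improvement in SD units):

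| Mean improvement (SD) | Truly improved | Labelled better half |
|---|---|---|
| −0.5 | 31% | 50% |
| 0 | 50% | 50% |
| 0.5 | 69% | 50% |
| 1.0 | 84% | 50% |

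The label does not move with the result. Apart from ties, it is always about 75 of 150.

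**6. Type I error.** With r = 0, simulation of the split gave 4.9%, so the test keeps its nominal level.

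**The case against.** The strongest reply is that this is a predictor analysis within the trained arms, that it leaves the randomised comparison untouched, and that it keeps its nominal error rate. All of that stands. Several stronger readings are tempting, and the documents do not support them.

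- **The split creates false predictors when nobody improved.** A reader might infer this, but it is not specific to the split. A regression slope does not depend on the mean change, so a linear model with zero average improvement would also find predictors of a relatively better outcome, and would find them more often because it has more power.
- **The split is on the end score, so the predictors found would be predictors of baseline severity.** The predictor sentence leaves this open. However, the same section defines the primary endpoints as change, and so does Primary outcome measures. Change is the natural reading, and what remains is a clarification of wording.
- **The plan labels half the children as successes and half as failures.** It does not use those words. The link between the split and learners comes from objective (ii). Because the Background describes neurofeedback as a learning paradigm, learner could also mean a child who acquires self-regulation of brain activity. The term is undefined, but no other analysis in the plan serves that objective.
- **A third of the information is lost, without condition.** That figure needs a roughly normal outcome. The plan says only that normality will be tested.

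**Conclusion.** The point holds as a loss of power and a limit on interpretation. With a roughly normal outcome and 150 children analysed, the split costs about 36% of the information. For predictors of modest strength (r = 0.20 to 0.30) that is about 11 to 20 points of power. The loss is smaller for heavy-tailed outcomes and larger for flat ones. With fewer children analysed, the same proportion is lost from a smaller base.

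Separately, and whatever the distribution, a sample-relative cut can support statements about who did relatively better but not about who improved. The plan contains no absolute criterion that could. The matter deserves correction because objective (ii) is a named key objective and the change is nearly free. It does not affect the validity of the main group comparison.

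**What to change.** In Statistical analysis, replace the median-split logistic regression with a linear regression of the continuous Conners 3 score. Name the scale and the time point. Fit one model per rater (parent, teacher, self), with that rater's baseline score as covariate and the listed predictors as regressors.

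This also removes the ambiguity between change and end score. If the end score is a + b × baseline + c × predictor, then change is a + (b − 1) × baseline + c × predictor, so the predictor coefficient c is the same either way.

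The model restores power but does not by itself show that anyone improved. If a learner/non-learner label is wanted, pre-specify an absolute reliable-change criterion calculated from the instrument's published reliability, and report it as secondary. The documents do not give that reliability, so it must be taken from the instrument's own documentation and stated. Such a label shows change beyond measurement error. It does not attribute the change to training, because the controls are outside this model.

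The cost is a change of wording with no new data, since the Conners 3 is already collected at baseline, post-training and follow-up. The small downside is that results are in score points, not odds ratios.
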